Title: Contribution of Endothelin-1 to Exercise Intolerance in Heart Failure
NCT Number: NCT02124824
Date: December 17, 2021

Study Objective: To compare the effect of Endothelin-1 on limb blood flow in patients with heart failure and healthy, age matched controls.

Study Design: Single arm, unblinded. Limb blood flow will be determined in patients with heart failure and healthy, age-matched controls.

Study Methods:

Limb Blood Flow: An ultrasound Doppler system (Logiq 7, GE Medical Systems, Milwaukee, Wisconsin, USA) equipped with a linear array transducer operating at an imaging frequency of 7-8 MHz and a Doppler frequency of 4-5 MHz will be used for determination of femoral artery diameter and blood velocity.

Study drug: The ET_A selective antagonist BQ-123 (0.6 mcg/dl/min) will be administered intra-arterially (common femoral artery) rest and during knee extensor exercise (0, 5, 10, and 15 Watts).

Statistical Analysis: Mixed model with repeated measures, with drug infusion at each work load is the dependent variable and HF (yes, no) and work load are the major predictor variables, with age and gender as additional explanatory variables. In a case where multivariate analysis is ultimately deemed appropriate and of interest, but the data do not satisfy the assumptions of normal distribution, we will invoke the central limit theorem and perform the bootstrap technique to estimate the bias and variation in the data and then correct accordingly. Because of the importance of ensuring a potential positive finding is not missed, no statistical adjustment will be made for multiple primary comparisons.

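### No masking is provided when limb blood flow is measured, so a reading error that differs between heart failure and controls would pass into the HF contrast

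*Combined protocol and SAP*

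**What the plan says.** All of this is in the combined protocol and SAP.

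- **Study Objective:** "To compare the effect of Endothelin-1 on limb blood flow in patients with heart failure and healthy, age matched controls".
- **Study Design:** the design is "Single arm, unblinded". The two groups are defined by disease status, not by randomisation.
- **Limb Blood Flow:** an ultrasound Doppler system "will be used for determination of femoral artery diameter and blood velocity". The section does not say who reads the images, whether reading is live, off-line or automated, or whether recordings are kept.
- **Study drug:** BQ-123 "will be administered intra-arterially (common femoral artery) rest and during knee extensor exercise". No off-drug recording is described.
- **Statistical Analysis:** "HF (yes, no) and work load are the major predictor variables", with age and gender added. The outcome is worded as "drug infusion at each work load is the dependent variable", which does not settle whether flow level, absolute change or percent change is analysed.

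No section mentions coded files, masked readers or locking of readings.

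**The concern.** The main contrast is HF against controls, and limb blood flow is the only outcome described. It is derived from two quantities that someone, or some software, must measure on an ultrasound image or trace. If a reader knows which group a recording comes from, readings may drift differently in the two groups.

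Such an error is aligned with the HF indicator. The model would estimate the true HF effect plus the error, and nothing among the planned predictors distinguishes the two. The bootstrap step cannot help either: resampling the recorded values carries the same group error into every resample. The protection has to be applied when the readings are made.

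How the error affects the result depends on the scale analysed, which the plan leaves open, so each scale is worked through separately.

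**Working it through.** The plan gives no reading error, SD, effect size or sample size, so it has no figure to reproduce. What follows is a sensitivity calculation on assumed inputs.

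**Inputs**
- From the plan: the measured quantities (diameter d, velocity v), the HF/control contrast, and the predictors.
- Assumed: flow = v × π(d/2)²; d = 0.9 cm; v = 8 cm/s off drug and 10 cm/s on drug; the same true values in both groups; reading error in HF only unless stated.
- True flow, multiplying by 60 for ml/min: off drug 8 × π × 0.45² × 60 = 305.4; on drug 10 × π × 0.45² × 60 = 381.7. The true absolute change is 76.3 ml/min and the true percent change is 10/8 − 1 = 25.0%.

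**1. Flow level, proportional error.** A diameter error b multiplies flow by (1+b)².
- b = 1%: 1.01² − 1 = 2.0%
- b = 2%: 1.02² − 1 = 4.0%
- b = 5%: 1.05² − 1 = 10.3%

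A velocity error of the same size shifts flow by 1%, 2% or 5%. Only the difference between groups matters: with 2% in HF and 1% in controls, the HF/control ratio moves by (1.02/1.01)² − 1 = 2.0%. With equal proportional errors it moves by 0.

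**2. Percent change, proportional error.**
- Same error at both infusions: 1.25 × (1+b)²/(1+b)² − 1 = 25.0%. The bias is zero.
- Error on drug only: the bias is 125 × ((1+b)² − 1) points, so 125 × 0.0201 = 2.5, 125 × 0.0404 = 5.05 and 125 × 0.1025 = 12.8 points for b = 1%, 2% and 5%.

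**3. Absolute change, proportional error, same at both infusions.** The change becomes 76.34 × (1+b)² = 77.88, 79.42 or 84.17 ml/min. Relative to the true 76.34, that is a bias of 2.0%, 4.0% or 10.3%, the same as for flow level. It does not cancel.

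**4. Additive error, same at both infusions.** Add c = 0.5, 1 or 2 cm/s to velocity.
- Flow level off drug shifts by c/8 = 6.3%, 12.5% or 25%; on drug by c/10 = 5%, 10% or 20%.
- Percent change becomes (10+c)/(8+c) − 1: 10.5/8.5 − 1 = 23.5%, 11/9 − 1 = 22.2% and 12/10 − 1 = 20.0%. The bias is −1.5, −2.8 or −5.0 points.
- Absolute change stays at 76.3 ml/min, because diameter is assumed equal at both infusions and the error is then additive in flow.
- An additive flow error of 50 ml/min gives (381.7 + 50)/(305.4 + 50) − 1 = 21.5% in place of 25.0%, again with absolute change intact.

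| Error in HF only, same at both infusions | Flow level | Absolute change | Percent change |
|---|---|---|---|
| Proportional | biased | biased by the same percentage | cancels |
| Additive in flow | biased | cancels | biased |

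**The case against.** **The text does not show that readers are unmasked.** The word stands under Study Design and can naturally be taken to describe the infusion. A reader might infer that the plan has flow read with knowledge of group, or that the results will be biased. The document supports neither: it is silent on how reading is done, and automated, operator-independent reading would make the concern much smaller. This stands, and it limits the point to an unaddressed risk.

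**The benefit of masking cannot be sized.** The errors above are assumed and cover scanning and reading together. Coded reading addresses only the reading part, and the plan gives no basis for splitting the two. This also stands.

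**Drug response might seem to be protected.** A reader might infer that percent response is at risk only if the error also differs by infusion, or that a constant error nearly cancels in absolute change. The first holds only for proportional errors (step 4 is the counterexample). The second is wrong for proportional errors (step 3). The plan specifies neither the scale nor the form of error, so neither reassurance is available.

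**Flow level on BQ-123 alone does not isolate the effect of Endothelin-1.** That is fair, but the absence of a described off-drug recording is a separate matter. The masking point does not depend on it, since every scale is exposed to at least one form of group-differential error.

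**Stored recordings and reader time are not mentioned in the plan.** Correct. The remedy is therefore conditional on recordings being saved, and asks for no additional reader.

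**Conclusion.** The point holds as a bias-reduction measure, not as a demonstrated error. The plan provides no masking for the measurement behind its only described outcome, and a reading error that differs by group could not be separated from the HF effect by the planned model.

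For illustration, an HF-only diameter error of 1%, 2% or 5% moves HF flow level, and absolute drug response if that is analysed, by 2.0%, 4.0% or 10.3%. Percent response is unaffected by a proportional error that is the same at both infusions, but not by an additive one. These figures rest on the assumed flow formula and assumed error sizes. With no SD, effect size or sample size in the document, they cannot be called large or small, and neither the size nor the direction of any actual bias can be estimated.

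**What to change.** Where recordings can be saved:

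1. Store diameter clips and velocity traces under random codes.
2. Have the staff who would read them anyway measure them off-line, in random order, without group labels (and without infusion labels if off-drug recordings exist).
3. Lock the readings before labels are merged.
4. In Study Design, replace 'unblinded' with 'open-label, with off-line measurement of limb blood flow masked to group'.

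If reading is already masked and off-line, or fully automated, the only change needed is a sentence saying so.

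**Cost:** file storage, random file names (a script can assign them), a locked reading sheet and a short delay before results can be viewed.

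**Limits:** a reader who also did the scan may recall it, group or work load may be recognisable from the image or trace, and bias at live acquisition is not removed.

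### Controls are matched on age but not sex, while the model adjusts for both; a difference in sex mix would cost precision in the HF effect, and frequency-matching on sex is a cheap safeguard

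*Combined protocol and SAP*

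**What the plan says.** The Study Objective sets the comparison: "To compare the effect of Endothelin-1 on limb blood flow in patients with heart failure and healthy, age matched controls". The Study Design repeats the control definition: "Limb blood flow will be determined in patients with heart failure and healthy, age-matched controls". In both places the selection criteria are health and age. Neither place mentions sex matching, a target sex ratio or recruitment by sex.

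Under Statistical Analysis, the repeated-measures mixed model is described thus: "HF (yes, no) and work load are the major predictor variables", "with age and gender as additional explanatory variables". Age is therefore handled by both recruitment and modelling, and sex by modelling only. No interaction with gender is named. The section also says that "no statistical adjustment will be made for multiple primary comparisons", and gives as its reason that a true finding should not be overlooked.

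The documents state no sample size, sex mix, standard deviation or effect size.

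**The concern.** HF status is not randomised, so the choice of controls is the main design protection for the HF comparison. The plan expects sex to be informative enough to belong in the model, yet its recruitment rule would allow a mostly male HF group beside a mixed-sex control group. The gender term would then have to separate two partly collinear variables.

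Two things are at stake:

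- **Precision.** The adjusted HF effect is built from within-sex contrasts. A sex that is scarce in one group supplies little information, however many of that sex are in the other group. For a plan that stresses not missing a true effect, avoidable variance works the wrong way.
- **Reliance on the model.** A single gender term assumes that the sex difference is the same at every work load and that the HF effect is the same in both sexes. With matched groups, departures from those assumptions matter less.

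**Working it through.** **Inputs.** From the documents: age-only matching; HF, work load, age and gender in the model; exercise loads of 0, 5, 10 and 15 Watts. Assumed here, because the documents give none: equal groups of n, the sex shares below, and the dependent variable read as the flow response during infusion. There is no figure in the plan to reproduce.

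**1. Variance of the sex-adjusted HF effect.** With male shares p1 (HF) and p0 (controls), mean share p, and phi the HF-sex correlation:

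phi² = (p1 − p0)² / [4p(1 − p)]; variance factor = 1 / (1 − phi²); SE factor = its square root.

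| HF male | Control male | phi² | Variance factor | SE |
|---|---|---|---|---|
| equal to controls | any | 0 | 1.00 | no change |
| 80% | 50% | 0.09/0.91 = 0.099 | 1.11 | +5% |
| 90% | 50% | 0.16/0.84 = 0.190 | 1.24 | +11% |
| 100% | 50% | 0.25/0.75 = 0.333 | 1.50 | +22% |
| 100% | 80% | 0.04/0.36 = 0.111 | 1.125 | +6% |

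Direct check of the 100%/50% row: the contrast is HF men against control men, with variance 1/n + 1/(n/2) = 3/n, against 2/n when matched. The ratio is 1.5.

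**2. Who carries the weight.** Each sex stratum is weighted by (HF count × control count) / (sum of the two). Take n = 10 per group:

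- 2 HF women and 5 control women: women 2×5/7 = 1.429, men 8×5/13 = 3.077. Each female control has weight (1.429/4.505)/5 = 0.063 and each male control 0.137.
- 1 and 5: 0.041 against 0.159.
- 0 and 5: exactly 0 against 0.200.

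**3. Repeated measures do not rescue this.** Generalised least squares with an assumed random-intercept correlation of 0.6, four loads, no women in the HF group and 5 of 10 controls female gives an HF variance of 0.21. That is 0.30 × (0.6 + 0.4/4). The matched value is 0.20 × 0.70 = 0.14, so the ratio is again 1.5. Without age in the model, female controls have weight 0 in the average HF effect. With age, the weight per observation is about 0.001 to 0.01, against 0.05 to 0.06 at most for male controls, and it arises only through the age slope.

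**4. Illustrative power.** Assume a difference of 1 SD, two-sided 0.05 and n = 20 per group. Power = Φ(1/√V − 1.96), with V = (2/20) × variance factor. Balanced: 0.885. At 80%/50% male: 0.851. At 100%/50% male: 0.733. With n = 10 per group the three values are 0.609, 0.565 and 0.447.

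**5. What a main-effect gender term leaves open.**

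- *Sex effect varying by load.* If HF-by-load terms are fitted with gender as a main effect only, female and male controls have equal weight in those contrasts (0.1 each at n = 10). If the change with load differs between the sexes by δ, the size of the error in the HF-by-load contrast is δ times the difference in female share: 0.3δ at 20% against 50% female, 0.5δ at 0% against 50%, and zero when the shares are equal.
- *HF effect varying by sex.* The single HF coefficient is a weighted average of the within-sex effects. With 2 HF women and 5 control women in groups of 10, the women's contrast has weight 1.429/4.505 = 0.32, although women are 20% of the HF group. With 2 and 2 it is 1/(1 + 4) = 0.20, which follows the enrolled HF group.

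**The case against.** The strongest reply is that the plan already puts gender in the model. Matching on one factor and adjusting for another is an accepted design. This stands for additive confounding. A sex difference in the response to BQ-123 is a difference in the outcome, and the gender term takes it out. A reader might infer from the age-only matching that the HF comparison is biased by sex. The documents do not support that unless the sex effect varies by load or the HF effect varies by sex.

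Second, no imbalance is shown. All the sex shares above are assumptions, and the larger losses need an HF group with few or no women beside controls who are about half female. At 80% against 50% male the cost is 5% in SE. The plan does not rule out sex matching in practice. This stands, and it is why the point is conditional.

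Third, a reader might conclude that female controls would be wasted. That holds only for the overall HF effect, and only if no HF patient is female. Otherwise they are down-weighted. Even in the extreme case they inform the age slope, the work-load effect and the residual variance.

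What the objection does not answer is precision and overlap: adjustment cannot supply within-sex comparisons that recruitment did not provide.

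**Conclusion.** The point holds as a cheap improvement, not as a demonstrated defect. Controls are matched on age only, while the model relies on both age and gender. If the groups differ in sex mix, the adjusted HF effect loses precision: SE +5%, +11% or +22% for an HF group 80%, 90% or 100% male, given equal group sizes, controls 50% male and an additive model. The actual loss cannot be stated, because the plan gives neither a sex mix nor a sample size, and it may be nil.

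There is a secondary exposure: HF-by-load contrasts and the meaning of the HF coefficient depend on interactions that the stated gender term does not cover. The plan does not say whether HF-by-load terms will be fitted.

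It would also go too far to infer that sex matching makes the result representative. It makes the weights follow the enrolled HF group's sex mix, which may itself differ from that of the HF population.

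**What to change.** In the Study Design, and consistently in the Study Objective, define the comparison group as *healthy controls frequency-matched to the HF group on age and sex*. Recruit controls against the running age-by-sex counts of enrolled HF patients. Keep age and gender in the model.

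If controls are already enrolled, fill any remaining places by sex and report the HF contrast in the sex strata present in both groups. If the HF group proves to be all of one sex, this adds little for the overall HF effect, which is then already a within-sex comparison. It would still keep any HF-by-load contrasts free of a sex difference.

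The cost is one line in the control definition and a recruitment tally, with no added participants or procedures. The downside is that volunteers whose age-by-sex cell is full are turned away, so control recruitment may be slightly slower.

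### The only specified model names drug infusion, not limb blood flow, as its response; read as flow during infusion, it has no BQ-123 contrast and cannot answer the objective

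*Combined protocol and SAP*

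**What the plan says.** The Study Objective is "To compare the effect of Endothelin-1 on limb blood flow in patients with heart failure and healthy, age matched controls". The Study Design section reads "Single arm, unblinded. Limb blood flow will be determined in patients with heart failure and healthy, age-matched controls". Under Limb Blood Flow in Study Methods, a Doppler ultrasound system "will be used for determination of femoral artery diameter and blood velocity". No other outcome is described.

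Under Study drug, BQ-123 "will be administered intra-arterially (common femoral artery) rest and during knee extensor exercise (0, 5, 10, and 15 Watts"). That makes five conditions: rest and four work loads. No saline, pre-infusion or other drug-free flow measurement is mentioned.

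The Statistical Analysis section specifies one repeated-measures mixed model, "with drug infusion at each work load is the dependent variable and HF (yes, no) and work load are the major predictor variables". The only other terms are the covariates age and gender. Limb blood flow is not mentioned there. No drug-condition term or interaction is listed. The later sentence on multivariate analysis and the bootstrap is a conditional fallback that gives no outcome and no terms, so it does not supply a second model.

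**The concern.** A dependent variable has to be something observed on the participant. Drug infusion is imposed by the investigators, so the model sentence cannot be fitted as written and the reader must guess the intended response. The guesses do not test the same thing.

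The objective is a difference of differences: how much blocking the ET-A receptor changes flow in heart failure, against how much it changes flow in controls. A model of flow recorded only during BQ-123 tests a simple group difference. A significant HF term could then reflect nothing more than a pre-existing difference in limb flow, and a null HF term could hide a real difference in response to the drug. Because the response is not fixed in advance, analysts could also fit different models to the same data and report different answers under the same sentence.

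**Working it through.** **Step 1. Set the sections side by side.**

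| Section | What it names |
|---|---|
| Study Objective | effect of Endothelin-1 on limb blood flow, HF against controls |
| Study Design | limb blood flow in both groups; single arm |
| Limb Blood Flow | femoral diameter and velocity |
| Study drug | BQ-123 at rest, 0, 5, 10 and 15 W; no drug-free condition stated |
| Statistical Analysis | response: drug infusion; predictors: HF, work load, age, gender |

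**Step 2. Three readings of the response.**

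1. *Literal.* The response is the infusion. Flow is not analysed.
2. *Flow during infusion.* Flow is analysed, with no drug contrast.
3. *Within-subject change in flow with BQ-123.* The HF term answers the objective with the predictors listed, but needs a drug-free measurement that the document does not describe.

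**Step 3. What reading 2 estimates.** Let m be mean drug-free flow and e the mean BQ-123 effect in each group. Then

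E[HF coefficient] = (m_HF + e_HF) − (m_C + e_C) = (m_HF − m_C) + (e_HF − e_C).

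The objective concerns only the second bracket. Data collected only during infusion cannot separate the two.

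**Step 4. Size under reading 2.** The plan has no figure to reproduce: it states no sample size, significance level, SD or drug-free flow. All inputs here are assumptions: 10, 15 or 20 per group, two-sided 5%, balanced complete data, age and gender ignored. Under these conditions the HF main effect is a two-sample t-test on each subject's mean flow over the five conditions, with df = 2n − 2 and noncentrality δ√(n/2), where δ is in SDs of subject-mean flow. For n = 10 and δ = 1, the noncentrality is 1 × √5 = 2.236.

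*False positive.* The drug effect is equal in both groups, so the true answer is zero. The probability that the HF term is significant is:

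| Drug-free difference | 10 per group | 15 per group | 20 per group |
|---|---|---|---|
| 0 | 0.050 | 0.050 | 0.050 |
| 0.5 SD | 0.185 | 0.262 | 0.338 |
| 1.0 SD | 0.562 | 0.753 | 0.869 |

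A Monte Carlo check (20,000 runs, correlation between drug and drug-free flow 0.7) gave 0.181 and 0.562 for 10 per group and 0.340 and 0.867 for 20. The change response rejected in 0.048 to 0.052 of runs.

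*Masking.* Drug-free flow is 1 SD lower in HF and BQ-123 raises flow 1 SD more in HF. The expected coefficient is −1 + 1 = 0, so it is significant in 5% of trials. For the change response the SD is √(2(1 − ρ)), with ρ the drug/drug-free correlation and equal SDs in the two conditions. At ρ = 0.6 this is 0.894, so δ = 1/0.894 = 1.118. Detection is:

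| ρ | 10 per group | 20 per group |
|---|---|---|
| 0.3 | 0.43 | 0.74 |
| 0.5 | 0.56 | 0.87 |
| 0.6 | 0.657 | 0.931 |
| 0.8 | 0.916 | 0.998 |

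**Step 5. Separate simulation under other assumptions.** This used 15 per group, four work loads, between-subject SD 1, residual SD 0.5 and 300 replicates.

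| True difference in drug effect | Drug-free flow in HF | HF term, infusion flow only: estimate, rejection | HF term, change in flow: estimate, rejection |
|---|---|---|---|
| 0 | 1 unit lower | −1.00, 73% | 0.01, 4% |
| 0.5 | 0.5 unit lower | 0.03, 4% | 0.51, 96% |

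**The case against.** The best defence is that this is loose wording. Limb blood flow is the only outcome described, and nobody would model an investigator-set infusion. The change reading arguably fits best: the objective concerns an effect, and leaving out a drug term is what one would write if the response were already the drug response at each work load. Under that reading the bias is zero. The document is a brief summary, and its silence does not show that drug-free flow goes unmeasured; a single-arm design can include measurements before and during infusion in the same person. Finally, every input to the size calculation is assumed, the masking case uses exact cancellation, and the gain from a change score shrinks at lower correlations.

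Much of this stands. The document does not show that a drug-free measurement is missing, only that none is stated. The single-arm label rules out a parallel drug-free arm, not a within-subject comparison. The error rates apply to one of three readings. At correlations of 0.3 to 0.5 the change response detects the masked effect in only 43% to 56% of trials with 10 per group.

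The concern survives all the same. Both the change score and its comparison condition have to be supplied by the reader, and the readings test different quantities. A statistical plan exists to settle that choice beforehand.

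**Conclusion.** The concern holds and must be fixed. The text is clear on two facts: the only specified model names an intervention as its response, and its predictors include no drug contrast. Read as flow during infusion, it gives the wrong answer to the objective whenever drug-free flow differs between groups. For a drug-free difference of 0.5 to 1.0 SD and no true difference in drug effect, the false-positive rate is about 19% to 56% with 10 per group, 26% to 75% with 15, and 34% to 87% with 20, against a nominal 5%. An opposite difference of equal size can reduce detection of a real effect to 5%.

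Confidence is high on the wording and the algebra. The percentages are illustrations on assumed sample sizes and differences, not estimates for this trial. The bias is zero if drug-free flow does not differ between groups, or if the response was always meant to be within-subject change.

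**What to change.** Name femoral (limb) blood flow as the dependent variable and define the comparison. Either form will do:

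- **Full model:** drug condition (BQ-123 or drug-free), HF, work load and the drug-by-HF interaction as fixed effects, with age and gender. The drug-by-HF term is the test of the objective.
- **Change model:** within-subject change in flow (BQ-123 minus drug-free) at each work load, with HF as the predictor of interest. No drug term is then needed.

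State whether drug-free flow is measured at rest and at each work load. If it is, only the Statistical Analysis wording changes. If it is not, neither model can be fitted without added measurements. The only cost-free correction is then to say that the analysis compares flow during BQ-123 between groups and cannot isolate the effect of Endothelin-1.
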